4.0 Recruitment Methods

4.1 Identification of subjects

Patients who present to the Emergency Department (ED) or who are already hospitalized at Hershey Medical Center (HMC) will be identified via the "brain attack" alert system. This system is updated in real-time when patients are having an acute IS in the ED or on the inpatient services of hospital. All stroke attending team physicians, residents, stroke fellows, the clinical stroke team and the stroke research coordinators are paged. All study personnel for this study have access to the brain attack alert system and will be notified. Upon presentation, all stroke patients have a neurological examination and are assessed using the NIHSS and the mRS as part of their routine care.

4.2 Recruitment process

4.2. 1 How potential subjects will be recruited.

Research team members will review the electronic medical record (EMR) for each patient arriving in the ED or presenting on the inpatient services at HMC with acute stroke-like symptoms for their eligibility to participate in this study.

4.2. 2 Where potential subjects will be recruited.

Potential subjects will be recruited in the Emergency Department (ED), inpatient or by telephone if the subject is found to be not capable of consenting for him or herself, and LAR is not present..

4.2. 3 When potential subjects will be recruited.

Potential subjects will be recruited prior to any study procedures taking place.

4.2. 4 Describe the eligibility screening process and indicate whether the screening process will occur before or after obtaining informed consent. Screening begins when the investigator obtains information about or from a prospective participant in order to determine their eligibility. In some studies, these procedures may not take place unless HIPAA Authorization is obtained OR a waiver of HIPAA Authorization when applicable for the screening procedures is approved by the IRB.

The EMR will be reviewed for inclusion/exclusion criteria prior to approaching a potential subject and/or subject's LAR.

5.0 Consent Process and Documentation

5.1 Consent Process:

Check all applicable boxes below:

- Informed consent will be sought and documented with a written consent form [Complete Sections 5.2 and 5.6]**
- Implied or verbal consent will be obtained – subjects will not sign a consent form (waiver of written documentation of consent) [Complete Sections 5.2, 5.3 and 5.6]**
- Informed consent will be sought but some of the elements of informed consent will be omitted or altered (e.g., deception). [Complete section 5.2, 5.4 and 5.6]**
- Informed consent will not be obtained – request to completely waive the informed consent requirement. [Complete Section 5.5]**

5.2 Obtaining Informed Consent

5.2. 1 Timing and Location of Consent

An approved study team member will meet with the subject and/or their LAR in a quiet private area. After careful and complete explanation of the study details, risks, and other options is provided to the subject and/or their LAR, a copy of the consent form will be provided to them for review. If they are interested in consenting to this study, they will be given additional time to ask questions. When all questions have been answered to their satisfaction by a study team member, the subject or their LAR will be asked to sign the informed consent document. A note will also be documented in the patient's medical record describing the process and discussion.

Telephone Consent Process

The physician/resident/ study coordinator will go to talk to potential subject and/ or family to determine if they are able to consent. If it is found that the potential subject cannot consent and their LAR is not present, an attempt to reach the LAR will be made to discuss the potential study enrollment. Whenever possible the potential subject will be present in the room while discussing the study over the phone with his/her LAR.

If there is interest by the potential subject's LAR we will continue to obtain information (email address, telephone or fax number, if available) so a copy of the consent and any other information can be sent to them.

The potential subject's representative (LAR) will be provided/sent a copy of the consent form and any other required information about the study, via email telephone, or fax, as requested by the LAR.

The physician and the study coordinator will conduct the telephone consent discussion with the subject's representative. This study involves greater than minimal risk, so we will have a witness present with the study team member during the telephone consent discussion. A review of the consent will be completed. All questions and concerns will be answered prior to the end of the discussion. Time will be given for the subject and/or subject's representative to review and discuss with other family members, if needed, prior to completion of the consent process.

The subject's representative will be asked if he/she would like to participate. If yes, the subject's representative will be asked to sign, date, time, and print their name on the consent form.

The subject's representative will be asked to return the signed consent form to the research site via email, phone text message with an attached picture of the signed consent page, or fax. If in route to the hospital, we will ask for the original signed document, as well. In order to return the signed document a telephone number, or email address, or fax number will be given to the subject's representative. A reminder of possible loss of

confidentiality may occur with email, telephone or fax, but we will be careful to give and review the telephone or fax number, and/or email address given to the subject and/or their representative.

We will begin study procedures once the signed copy of the consent form is received from the subject's representative via email, text message with photo attachment of signed consent, or fax.

The team member obtaining informed consent will complete and sign a Signature Page for Telephone Consent Process, which was approved by the IRB.

A complete copy of the signed consent form and the signed Signature Page for Telephone Consent Process will be given to the subject's representative. The signed copies may be given to the subject's representative in-person or sent to the subject's representative by email, mail or fax, depending on how the subject's representative requests the signed documents to be sent to them

The phone consent procedure should be included in the note to file used to document the informed consent process in the research record or medical record. A copy of the signed consent form will be placed in the medical record and given to the subject.

All subjects will be required to assent when able to sign an informed consent form. The same consenting process will be completed with the subject – the discussion will be maintained in a private setting, he/she will be given time to review and discuss the research study and consent with his/her family. Questions will be answered and LAR will be present during the discussion.

5.2. 2 Coercion or Undue Influence during Consent

The study will first be introduced to subjects by one of the clinical investigators. The study coordinator or other member of the study team who is not directly involved in the clinical care of the patient will meet with the subject for a detailed discussion of the study and to complete the consent process.

Study team members will stress that participation is completely voluntary. Additionally, it will be carefully and clearly explained that if they should decide not to participate in this study, that decision will have no impact on the care the patient will receive.

5.3 Waiver of Written Documentation of Consent

Not applicable

5.3. 1 Indicate which of the following conditions applies to this research:

The research presents no more than minimal risk of harm to subjects and involves no procedures for which written consent is normally required outside of the research context.

OR

The only record linking the subject and the research would be the consent document and the principal risk would be potential harm resulting from a breach of confidentiality. Each subject will be asked whether the subject wants documentation linking the subject with the research, and the subject's wishes will govern.

OR

If the subjects or legally authorized representatives are members of a distinct cultural group or community in which signing forms is not the norm, that the research presents no more than minimal risk of harm to subjects and provided there is an appropriate alternative mechanism for documenting that informed consent was obtained.

Describe the alternative mechanism for documenting that informed consent was obtained:

5.3. 2 Indicate what materials, if any, will be used to inform potential subjects about the research (e.g., a letter accompanying a questionnaire, verbal script, implied consent form, or summary explanation of the research)

5.4 Informed consent will be sought but some of the elements of informed consent will be omitted or altered (e.g., deception).

Not applicable

5.4. 1 Indicate the elements of informed consent to be omitted or altered

5.4. 2 Indicate why the research could not practicably be carried out without the omission or alteration of consent elements

5.4. 3 Describe why the research involves no more than minimal risk to subjects.

5.4. 4 Describe why the alteration/omission will not adversely affect the rights and welfare of subjects.

5.4. 5 If the research involves using identifiable private information or identifiable biospecimens, describe why the research could not be practicably be carried out without using such information or biospecimens in an identifiable format.

5.4. 6 Debriefing

5.5 Informed consent will not be obtained – request to completely waive the informed consent requirement

Not applicable

5.5. 1 Indicate why the research could not practicably be carried out without the waiver of consent

5.5. 2 Describe why the research involves no more than minimal risk to subjects.

5.5. 3 Describe why the alteration/omission will not adversely affect the rights and welfare of subjects.

5.5. 4 If the research involves using identifiable private information or identifiable biospecimens, describe why the research could not be practicably be carried out without using such information or biospecimens in an identifiable format.

5.5. 5 Additional pertinent information after participation

5.6 Consent – Other Considerations

5.6. 1 Non-English-Speaking Subjects

At this time, we do not anticipate enrolling any non-English speaking subject. However, if we do, an approved short form or oral translation process will be used to obtain informed consent.

5.6. 2 Cognitively Impaired Adults

5.6.2.1 Capability of Providing Consent

All stroke patients undergo a detailed neurological examination by the treating physician team which includes an assessment of their capacity to give informed consent.

In addition potential study subjects will be evaluated by a study team member for any cognitive or language impairment or other physical limitations that does prevent him/her from making a reasoned, informed decision. All members of the research team have prior experiences in participating in acute stroke research.

5.6.2.2 Adults Unable to Consent

This study involves individuals who have an ischemic stroke. Due to the type of the insult, these individuals may be compromised and unable to communicate. If the subject is unable to provide consent, the research team will obtain informed consent from an (LAR). The LAR will be defined as a court-appointed legal guardian, a health care power of attorney or a health care representative.

5.6.2.3 Assent of Adults Unable to Consent

All subjects who are physically able to provide assent will be asked if unable to sign an informed consent form. The same consenting process will be completed with the subject – the discussion will be maintained in a private setting, he/she will be given time to review and discuss the research study and consent with his/her family. Questions will be answered and an impartial individual or LAR will be present during the discussion.

5.6.3.1 Parental Permission

5.6.3.2 Assent of subjects who are not yet adults

6.0 HIPAA Research Authorization and/or Waiver or Alteration of Authorization

6.1 Authorization and/or Waiver or Alteration of Authorization for the Uses and Disclosures of PHI

Check all that apply:

- Not applicable, no identifiable protected health information (PHI) is accessed, used or disclosed in this study. [Mark all parts of sections 6.2 and 6.3 as not applicable]
- Authorization will be obtained and documented as part of the consent process. [If this is the only box checked, mark sections 6.2 and 6.3 as not applicable]
- Partial waiver is requested for recruitment purposes only (Check this box if patients' medical records will be accessed to determine eligibility before consent/authorization has been obtained). [Complete all parts of sections 6.2 and 6.3]
- Full waiver is requested for entire research study (e.g., medical record review studies). [Complete all parts of sections 6.2 and 6.3]
- Alteration is requested to waive requirement for written documentation of authorization (verbal authorization will be obtained). [Complete all parts of sections 6.2 and 6.3]

6.2 Waiver or Alteration of Authorization for the Uses and Disclosures of PHI

6.2. 1 Access, use or disclosure of PHI representing no more than a minimal risk to the privacy of the individual

6.2 .1.1 Plan to protect PHI from improper use or disclosure

Information is included in the "Confidentiality, Privacy and Data Management" section of this protocol.

6.2 .1.2 Plan to destroy identifiers or a justification for retaining identifiers

Minimal screening activities prior to consent may include accessing patient charts to confirm eligibility. No identifiers will be retained for any patient who does not meet eligibility requirements or whose LAR does not provide consent to participate in the study.

6.2. 2 Explanation for why the research could not practicably be conducted without access to and use of PHI

The study requires the screening of patients identified through the brain attacks call system to evaluate them for potential participation in this study. This prescreen takes place prior to study enrollment. Depending on their diagnosis, they may be able to be enrolled in the study once a quick review of their chart is completed, in order to permit a review of inclusion/exclusion criteria. A partial waiver is needed to recruit the patients that meet criteria for the study.

6.2. 3 Explanation for why the research could not practicably be conducted without the waiver or alteration of authorization

There is a short (18 hour) window in which patients are eligible for enrollment and the waiver will allow the study staff and/or coordinator to review the chart as soon as possible, in order to assist in the recruitment process.

6.3 Waiver or alteration of authorization statements of agreement

Protected health information obtained as part of this research will not be reused or disclosed to any other person or entity, except as required by law, for authorized oversight of the research study, or for other permitted uses and disclosures according to federal regulations.

The research team will collect only information essential to the study and in accord with the 'Minimum Necessary' standard (information reasonably necessary to accomplish the objectives of the research) per federal regulations.

Access to the information will be limited, to the greatest extent possible, within the research team. All disclosures or releases of identifiable information granted under this waiver will be accounted for and documented.

7.0 Study Design and Procedures

7.1 Study Design

This double-blinded, randomized, placebo-controlled pilot study will evaluate the effects of acute PGZ treatment on clinical outcomes and markers of the stress-immune response in hyperglycemic patients (blood glucose ≥ 150 mg/dl at the time of presentation) who present with acute IS symptoms within 18 hours of symptom onset or their last known time being well. In addition feasibility and safety of acute PGZ treatment in stroke patients with hyperglycemia will be established.

Study enrollment will not delay administration of standard of care stroke therapies, such as thrombolysis and/or thrombectomy. If patients undergo a thrombectomy prior to study enrollment, the blood sugar level will be rechecked after the procedure to ensure that patients still meet the criteria to participate in this study (blood glucose ≥ 150 mg/dl).

To study the effects of PGZ on the immune system, we will collect blood from all study participants before initiation of study drug and 24 hours after each dose of study drugs. The following will be performed:

- Measurement of immune cells: Absolute counts of neutrophil, monocytes and lymphocytes will be measured by performing differential counts on blood smears of blood samples from study participants and by flow cytometry.
- Measurement of activated neutrophils and monocytes: We will measure the neutrophil and monocyte activation activated cell surface markers by flow cytometer and data will be analyzed using FlowJo software Tree Star, Inc.

- Neutrophil function: Neutrophil function will be measured by phagocytosis assay and oxidative burst using flow cytometry.
- Annexix A1, apoptotic and anti-apoptotic markers: Apoptotic marker caspase 3-PE, anti-apoptotic factor MCI-1 FITC and Annexin A1-APC will be measured by flow cytometry.
- Cytokine assay: Pro-inflammatory circulating cytokines (TNF α , IL-1 α , IL-1 β , IL-2, IL-6, IL-10 which are known to be up-regulated after ischemic stroke will be measured by Bio Plex multiplex immunoassays.
- Serial measurements of Insulin and Glucose levels, cortisol, catecholamines ESR and hsCRP will be performed.
- An additional blood sample will be stored for future biomarker analysis.

7.2 Study Procedures

7.2. 1 Baseline

Baseline activity will occur within 18 hours of symptom onset (or last known well time) and will include screening, enrollment, randomization, medical history, physical and neurological examinations, clinical assessments (including the NIHSS, mRS, BI, GCS and MOCA), collection of blood biomarkers and liver function tests.

1. **Screening and Enrollment:** The study will enroll participants over one year. Each patient in the ED or on the inpatient service who presents with acute stroke-like symptoms and/or suspected cerebral infarction within 18 hours of symptom onset or their last known time being well, will be identified and screened for the study. The time of symptom onset will be determined based on discussion between the clinical care team and the patient, the patient's care givers and the treating physicians. If the stroke onset time is not known, such as when a patient awakens with stroke symptoms, the last known time when the patient was well will be defined as onset time. Acute ischemic stroke (AIS) will be diagnosed based on non-contrast head CT, perfusion head CT and/or brain MRI or based on neurological assessment, all of which is part of the routine assessments by the clinical physician team. The severity of stroke will be determined by the NIHSS and mRS, which are completed by the treating physicians at time of presentation.

Prior to performing any study-related activities, written informed consent will be obtained from the subject or the subject's LAR. The background of the proposed study, all study procedures, the benefits and risks of the study, and that study participation is voluntary for the subject will be explained to the subject or the subject's LAR, who will be given sufficient time to consider whether to participate in the study.

After obtaining written consent, the subject's data will be collected from the medical record for research purposes.

2. **Randomization:** After obtaining written consent, subjects will be randomized to either the PGZ or placebo treatment arm of the study using an equal allocation ratio (1:1). See section 7.4.3.
3. **Pretreatment assessments:** Prior to the administration of the investigational product, the following will be done.

The following standard of care data will be **collected from the EMR for research purposes:**

- Demographic information (age, gender, race, contact information)

- Medical history
- Admission diagnoses
- Time of symptom onset or last known well time
- Current medication usage
- Results from the standard care laboratory workup including complete blood count, coagulation studies, basic metabolic panel (including serum glucose, renal function, and electrolytes), and if applicable results of pregnancy test and urinary drug screen)
- Health care services rendered (diagnostic workup procedures, use of t-PA, and thrombectomy, use of antibiotics, treatment of cerebral edema and hemorrhagic conversion)
- Images and results of the interpretation of the neuroimaging studies (brain MRI and head CT)
- NIHSS and mRS scale

The following assessments will be **performed only for research**:

- BI, GOS will assess neurological outcomes and will be performed by certified study personnel.
- MOCA will assess cognitive function and will be performed by certified study personnel.
- Blood will be collected (approximately 15 mls.) for the following tests:
 - ESR, hsCRP, CBC with differential, blood glucose, insulin, cortisol and catecholamines
 - T Cells, B cells, activated myelocytes
 - Inflammatory markers, cytokines, apoptotic markers
 - Other biomarkers.
 - AST, ALT and total bilirubin

4. Administration of the Investigational Product: Study treatment administration will be initiated within 18 hours after the onset of stroke symptoms or last known well time. Liver function tests (serum ALT, AST, and total bilirubin) will be assessed prior to initiating study drug treatment. The treatment group will receive a 45 mg Pioglitazone capsule orally every 24 hours for 3 days for a total of 3 doses. The control group will receive placebo at the same time points. Both groups will be treated identically and receive best standard of care.

If subject will be unable to swallow the study drug, will be administered via feeding tube (See study drug detailed in sections 7.4.2 and 7.4.5).

In addition, for research purposes finger stick glucose measurements will be performed 2h after initial study drug administration (time of peak of PGZ concentration) and subsequently at regular time points as determined by the standard of care protocol for stroke patients (see attached standard of care protocols for hypoglycemia and hyperglycemia for acute stroke patients, Appendix 1).

7.2. 2 Day 1

This will occur 24 (+/- 2) hours after the initial dose of the investigational product is administered. At this time, the following **research-only activities** will occur:

- AEs and concomitant medications will be documented.
- Prior to administration of the investigational product, blood will be collected (approximately 10 mls) for the following tests: ESR, hsCRP, CBC with differential, blood

glucose, insulin, cortisol and catecholamines, T Cells, B cells, activated myelocytes, inflammatory markers, cytokines, apoptotic markers, other biomarkers.

- The second dose of investigational product will be administered.

7.2. 3 Day 2

This will occur 24 (+/- 2) hours after the second dose of investigational product is administered.

At this time, the following **research-only activities** will occur:

- AEs and concomitant medications will be documented.
- Prior to administration of the investigational product, blood will be collected (approximately 10 mls) for the following tests: ESR, hsCRP, CBC with differential, blood glucose, insulin, cortisol and catecholamines, T Cells, B cells, activated myelocytes, inflammatory markers, cytokines, apoptotic markers, other biomarkers.
- Prior to administration of the investigational product, blood will be collected (approximately 5 mls) and sent for liver function testing (AST, ALT and total bilirubin). Liver function test results will be confirmed prior to the administration of the investigational product.
- The third dose of investigational product will be administered.

7.2. 4 Day 3

This will occur 24 (+/- 2) hours after the third dose of investigational product is administered.

This may occur at the discharge visit, if that occurs prior to the scheduled day 3 visit. At this time, the following **research-only activities** will occur:

- AEs and concomitant medications will be documented.
- Blood collection (approximately 10 mls) for the following tests: ESR, hsCRP, CBC with differential, blood glucose, insulin, cortisol and catecholamines, T Cells, B cells, activated myelocytes, inflammatory markers, cytokines, apoptotic markers, other biomarkers.

7.2. 5 Discharge

This will occur on the day of discharge from the hospital. A standard of care routine physical and neurological examination will be conducted. The following assessments will be performed;

- NIHSS and mRS scale
- BI, GOS (for research only)
- MOCA (for research only)
- AEs and concomitant medications will be documented for **research-only**.

7.2. 6 Day 90 Visit

This visit will occur 90 days (+/- 30 days) from the day of discharge. A standard of care routine physical and neurological examination will be conducted. If the patient is unable to travel to the clinic, the following assessments may be done via phone call:

- NIHSS and mRS scale
- BI, GOS (for research only)
- MOCA (for research only)
- AEs and concomitant medications will be documented for **research-only**.

Schedule of Study Activities

	Baseline (0-18h from symptom onset)	Day 1: 24+/-2h after first dose of study drug/ placebo 24 hrs	Day 2: 24+/-2h after second dose of study drug/ placebo	Day 3: 24+/-2h after third dose of study drug/ placebo	Discharge	Day 90: ± 30 days follow-up visit

Screening/Enrollment	X					
Informed consent	X					
Administration of study drug or placebo	X	X	X			
Clinical scales: NIHSS, mRS, BI, GOS, MOCA	X				X	X
Blood for laboratory tests and biomarkers	X (pre-treatment)	X (pre-treatment)	X (pre-treatment)	X		
Liver function test	X (pre-treatment)		X (pre-treatment)			
Medical history	X (pre-treatment)					
Physical and neurological examination	X (pre-treatment)				X	X
AEs and concomitant Medications		X	X	X	X	X
Blood glucose assessment via finger stick	X*					

BI = Barthel Index; GOS = Glasgow Outcome Scale; MOCA = Montreal Cognitive Assessment; mRS = modified Rankin Scale; NIHSS = NIH Stroke Scale

*finger stick glucose measurements will be performed 2h after initial study drug administration (time of peak of PGZ concentration) and subsequently at regular time points as determined by the standard of care protocol for stroke patients (see attached standard of care protocols for hypoglycemia and hyperglycemia for acute stroke patients, Appendix 1).

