1.0 Objectives

1.1 Study Objectives

The long term objective of this study is to determine whether Pioglitazone (PGZ) can improve clinical outcomes in hyperglycemic acute ischemic stroke (IS). We propose to study the efficacy of PGZ treatment and its effects on the peripheral immune-stress response in hyperglycemic stroke patients within a randomized, placebo controlled, double-blinded clinical pilot study with two objectives:

- 1. Study the effects of acute PGZ treatment on clinical outcomes at three months after stroke:** Well validated assessment tools of neurological function, including the NIH Stroke Scale (NIHSS), modified Rankin scale (mRS), Barthel index (BI) and Glasgow Outcome Scale (GOS) will be used to assess neurological outcomes. In addition, cognitive function will be assessed by the Montreal Cognitive Assessment (MOCA), and data on in-hospital and after discharge infection rates, re-hospitalization rates, stroke volume and all-cause mortality will be collected.
- 2. Explore whether acute treatment with PGZ can improve outcomes in hyperglycemic stroke by modulation of the stress-immune response.** We will measure how PGZ changes blood concentrations of insulin, glucose, cortisol and catecholamines after initiation of treatment. Based on our preliminary preclinical studies, we hypothesize that PGZ will decrease circulating levels of activated neutrophils and monocytes, improve neutrophil function, decrease cytokine levels, normalize the N/L ratio and increase the anti-inflammatory annexin A-1 pathway, all of which are altered in the hyperglycemic state.

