1.2 Primary Study Endpoints

The primary objectives of this pilot study are 1) to determine whether PGZ can improve outcomes at 3 months post-stroke in hyperglycemic acute ischemic stroke, and 2) to study whether there is association between immune-stress response modulation and clinical outcomes after treatment of PGZ following acute ischemic stroke in hyperglycemic patients.

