3.3 Early Withdrawal of Subjects

3.3. 1 Criteria for removal from study

Patients with a need for treatment with immunomodulatory drugs or those who develop any new conditions described in the exclusion criteria during treatment phase of clinical trial will be removed from the study. Additionally, cognitively impaired subjects will be withdrawn if they are unduly distressed as required by IRB policies.

3.3. 2 Follow-up for withdrawn subjects

Subjects will be withdrawn from the study if the study subject or Legally Authorized Representative (LAR) withdraws consent for any reason. The primary reason for the subjects' withdrawal from the study will be recorded.

If a subject is withdrawn due to pregnancy, experiences an adverse event (AE), a medical emergency, or is unwilling or unable to comply with the protocol, he/she must undergo a 90 day assessment unless the withdrawal is due to death or the withdrawal of consent. Subjects who withdraw from the study may be replaced.

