9.4 Frequency of data collection

The data of neurological function (NIHSS, BI, mRS, GOS and MOCA) will be collected before initiation of study drug, at discharge from hospital, and at 90 days during the follow-up visit. Inflammatory markers and all biomarkers will be collected at baseline and 24 hours after each dose of study drug for three consecutive days (see also table of study events, section 7.2).

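### The objectives set the clinical outcome at three months after stroke, but section 7.2.6 counts the Day 90 visit from hospital discharge and no other passage reconciles the two

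*Combined protocol and SAP*

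**What the plan says.** Objective 1 in section 1.1 is to "Study the effects of acute PGZ treatment on clinical outcomes at three months after stroke". Section 1.2 repeats the time point as a primary objective: "to determine whether PGZ can improve outcomes at 3 months post-stroke in hyperglycemic acute ischemic stroke". Both count from the stroke.

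Section 7.2.6 defines the visit at which those outcomes are measured: "This visit will occur 90 days (+/- 30 days) from the day of discharge". This is the only sentence in the protocol that gives the visit a starting point.

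The other places that mention the time point are silent on the anchor:

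- **Schedule of Study Activities.** The Baseline column begins "Baseline (0-18h from symptom onset", and the Day 1 column is timed "24+/-2h after first dose of study drug/ placebo", with Days 2 and 3 following the same pattern. The last column says only "Day 90: ± 30 days follow-up visit".
- **Section 9.4.** The scales are collected before study drug, "at discharge from hospital, and at 90 days during the follow-up visit".
- **Section 3.3.2.** For certain withdrawn subjects, "he/she must undergo a 90 day assessment unless the withdrawal is due to death or the withdrawal of consent". No starting point is given.
- **Section 7.3.** Participation lasts about three months in total, and the follow-up takes place at the routine neurology clinic appointment.
- **Section 8.3.** The scales at three months are compared with admission, with no visit window or date rule.

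**The concern.** Stroke and discharge are different days, and the gap between them varies from patient to patient. Discharge also comes after randomisation, so its date can depend on severity, complications and, in principle, treatment. Section 4.1 lets patients who are already in hospital enter the study, and their discharge may be governed by another illness. Counting from discharge makes time since stroke at the primary assessment a function of length of stay.

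This visit carries primary objective 1, and section 8.2 intends the data to inform the power analysis of a later trial. If the assessment is not at the time point that the objectives name, the estimate taken forward is described inaccurately. Withdrawn subjects add to the ambiguity: staff could count their 90 days from onset, discharge or withdrawal.

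**Working it through.** The plan states no figure to reproduce, so the check works out what 7.2.6 implies in days after stroke.

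**Inputs from the documents.** Target 90 days and tolerance 30 days either side, counted from discharge (7.2.6); 22 patients per group, 44 in total (8.2).

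**Assumptions.** L, the days from stroke to discharge, is not given. I use 3, 7, 14 and 21 days and, where an average is needed, L uniform over 3 to 21. Visits either spread evenly over the window or cluster around target with an SD of 7 days.

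**Timing after stroke.** Earliest L+60, target L+90, latest L+120. If visits spread evenly, the share falling after day 120 is L/60. If they cluster, it is 1 − Φ((30 − L)/7).

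| L (days) | Earliest | Target | Latest | After day 120, even spread | After day 120, SD 7 |
|---|---|---|---|---|---|
| 3 | 63 | 93 | 123 | 5% | <0.1% |
| 7 | 67 | 97 | 127 | 12% | <0.1% |
| 14 | 74 | 104 | 134 | 23% | 1.1% |
| 21 | 81 | 111 | 141 | 35% | 9.9% |

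Day 90 after stroke stays inside the permitted window as long as L+60 ≤ 90, that is, for stays of up to 30 days.

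**Where the spread comes from.** The full range is 141 − 63 = 78 days. Of these, 60 come from the tolerance and 21 − 3 = 18 from the anchor.

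**What re-anchoring gains.** The variance of L is 18²/12 = 27. The variance of an even window is 60²/12 = 300.

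- Even spread: the SD of time since stroke falls from √(27 + 300) = 18.1 to √300 = 17.3 days.
- Clustered visits: it falls from √(27 + 49) = 8.7 to 7.0 days.

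**Could the anchor bias the comparison?** With 22 per arm the standard error of a standardised difference is √(2/22) = 0.302 SD. Assume that mean L differs by 5 days between arms. To move the comparison by one standard error, recovery would have to run at 0.302/5 = 0.060 SD per day, or 0.060 × 60 = 3.6 SD over 60 days. That is implausibly steep.

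**Visits affected by the fix.** Averaged over L uniform on 3 to 21, the share of discharge-booked visits after day 120 is 12/60 = 20% under even spread (0.20 × 44 = 8.8, about 9 patients) and 1.8% under clustering (0.018 × 44 = 0.8, about 1 patient).

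**The case against.** The strongest reply is that this is a small matter in an exploratory pilot. For stays of 3 to 7 days the target is day 93 to 97, which most readers would call three months. The wide tolerance dominates the spread, and re-anchoring leaves it untouched. This stands, and it limits how much weight the point can bear.

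Second, the discharge anchor may have a practical reason. Section 7.3 ties the visit to the routine clinic appointment, and objective 1 includes infections after discharge and re-hospitalisation, for which discharge is a natural origin. The protocol does not state this reason, but it is plausible. It does not remove the conflict: the functional scales are still promised at three months after stroke. The participation length in 7.3 does not settle the anchor either, since it is approximate and the tolerance alone carries even a stroke-anchored visit to day 120.

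Third, the schedule table summarises 7.2.6, so its silence is not a separate defect. That is fair. The conflict lies between 7.2.6 and sections 1.1 and 1.2; the silent passages matter only because none of them resolves it.

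Fourth, the sizes depend on assumed stays. Section 7.2.4 foresees discharge before the Day 3 visit, so some stays may be shorter than the range used here, which would shrink the effect.

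**Conclusion.** The inconsistency is real and unresolved. Sections 1.1 and 1.2 count from stroke; 7.2.6 counts from discharge. As written, the visit falls on day L+60 to L+120 after stroke, with a target of day 93 to 111 for assumed stays of 3 to 21 days. It should be corrected, but the gain is modest: the SD of time since stroke drops by 0.8 to 1.7 days under the assumptions above.

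A reader might infer two stronger things, and the documents support neither. One is that discharge anchoring biases the treatment comparison because discharge follows randomisation. The mechanism exists, but nothing in the documents indicates a difference in stay between arms, and a 5-day difference would need an implausible recovery slope to matter. The other is that patients are in fact being assessed at the wrong time. The documents show only what is written, not how visits are booked, and day 90 after stroke remains within the window for any stay of up to 30 days.

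The case for change rests on the mismatch between the stated endpoint and the visit that measures it.

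**What to change.** In 7.2.6 and the schedule table, define Day 90 as 90 days (± 30 days) from symptom onset or last known well, as set out in 7.2.1. Use the same anchor in 9.4 and for the 90 day assessment in 3.3.2. Record the date of each assessment, and report time since onset by arm.

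The onset time is already defined and collected at baseline, so the text changes are short. The cost is operational. Because the visit uses the routine clinic appointment, some visits booked from discharge would fall after day 120 and need an earlier slot: about 2% to 20%, or 1 to 9 of 44 patients, under the assumed stays. The telephone option does not cover these cases as written, since 7.2.6 offers it only to patients who cannot travel. Using it for late appointments would be a protocol change and should be presented as one.

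Infections after discharge and re-hospitalisation can still be reported from the day of discharge, using the recorded dates.
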